4.10 Secondary Endpoint Analyses

Additionally, change from Baseline in WOMAC A pain score will be analyzed separately at each visit through Week 26 using an ANCOVA model with effect treatment and covariates site,

	CLR_17_17 Statistical Analysis Plan	
	Date: 30-Sep-2022	Page 20 of 28

VAS knee pain and global pain scores are collected daily. Weekly post-baseline average daily scores will be calculated for all weeks through Week 26 regardless of whether or not there was a scheduled visit at that week. Weeks will be calculated according to actual study days. Since the Day 1 assessment is scheduled to be collected prior to dosing, Week 1 will be calculated from VAS scores collected on Days 2 through 8, Week 2 from Days 9 through 15, etc. Daily VAS global pain score is only collected prior to dosing on Day 1. Per the definition of baseline in Section 5.1, the last daily VAS global pain score collected prior to the date and time of dosing will be considered baseline for the change from baseline analyses. Daily VAS knee pain score is collected daily leading up to Day 1. Baseline daily VAS knee pain score will be calculated as the average of the assessments on Day 1, if prior to dosing, and the previous six days. Day 1 assessments of average daily knee pain and average daily global pain that are collected after dosing will be excluded from baseline and the Week 1 daily average determination. Weekly averages will be calculated based on the number of days in the week with non-missing pain scores.

The weekly cumulative amount of rescue medication will be based on information from the rescue medication dispensing and accountability eCRF pages only. Weekly cumulative amount of rescue medication will be calculated between each scheduled visit. At each visit, rescue medication is returned and accounted for from the previous visit and new rescue medication is dispensed. It will be assumed that no rescue medication was taken on the day of return unless rescue medication was also dispensed on that date. If so, then the dosage taken for that day will be based on the accountability for the newly dispensed rescue medication. The amount of rescue medication taken between visits will be based on the “number of tablets consumed” and the associated “dosage per tablet” as captured on the eCRFs. For a given period (dispensing through return), the average daily dose of rescue medication will be calculated. It will be assumed that the subject consumed this average daily dose of rescue medication on each date in the period. Dates for which a subject is in the study, but do not fall within one of the dispensing and return periods or the date of return where no new rescue medication was dispensed, will be assumed to have no rescue medication received. The days associated with a given visit include the date of the previous visit through the day prior to the current visit. Weekly cumulative amount of rescue medication for a given visit will be calculated by summing up the daily doses within the period, dividing by the number of days in the period, and then multiplying by seven. Subjects with missing information for a given period will have their weekly cumulative amount of rescue medication set to missing for that period. Subjects discontinuing early will be analyzed in the MMRM analysis only through the last scheduled visit. However, rescue medication usage after this visit through the date of early termination will be summarized under the heading “Last Visit”. Subjects completing the study

	CLR_17_17 Statistical Analysis Plan	
	Date: 30-Sep-2022	Page 21 of 28

that have a calculable Week 26 weekly cumulative amount of rescue medication will have their Week 26 results summarized under Week 26 and “Last Visit”.

[REDACTED]

[REDACTED]

[REDACTED]

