2. STUDY OBJECTIVES AND ENDPOINTS

Primary Efficacy Objective	Endpoint(s)
To determine the optimal dose of an IA joint injection of MM-II in the treatment of knee pain in subjects with symptomatic knee OA	Change from Baseline of WOMAC A pain score at Week 12
Primary Safety Objective	Endpoint(s)
To assess the safety and tolerability of a single IA joint injection of MM-II in the treatment of knee pain in subjects with symptomatic knee OA at Week 12	
• AEs• Laboratory assessments• Vital signs• ECG• Physical examination

Secondary Objectives	Endpoint(s)
To assess the effect of a single IA joint injection of MM-II in subjects with symptomatic OA	
• [REDACTED]• [REDACTED]• Change from Baseline in the weekly average of daily knee pain scores by Visual Analog Scale (VAS) at Weeks [REDACTED] 26, [REDACTED]• Change from Baseline in the weekly average of daily global pain scores by VAS at Weeks [REDACTED] 26, [REDACTED]
[REDACTED]	[REDACTED]

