5. DATA HANDLING

5.1 Baseline, Pre-Dose, and Study Visits

Baseline daily VAS knee pain score will be calculated as the average of the assessments on Day 1 and the previous six days. For all other parameters, the last non-missing value, including unscheduled, of a variable taken before the single dose of IP will be used as the Baseline value. Except for determination of the PK parameters, all post-Baseline unscheduled data will be excluded from the analyses and presented in the listings only. Except for pharmacokinetic concentration data used to derive PK parameters, which will be analyzed at the actual sampling times, including unscheduled, all other analyses presented by collection day and/or by time point will be based on the schedule of assessments as planned in the protocol and recorded on the eCRFs. However, subjects who prematurely discontinue from the study having their final visit assessments collected on the Week 26 eCRFs. For these subjects, data collected under Week 26 will be mapped to one of the scheduled visits based on the following visit windows. On a per data point basis, if no scheduled result exists for the mapped visit, then the Week 26 will be used in the analysis for

that visit. If there is a scheduled result associated with the mapped visit, then the original scheduled result for that visit will be used in the analysis and the mapped Week 26 result will be presented in the listings only.

Visit	Target Study Day	Study Day Range
Week 1 ^a	8	1 – 11
Week 2	15	12 – 22
Week 4	29	23 – 43
Week 8	57	44 – 71
Week 12	85	72 – 99
Week 16	113	100 – 127
Week 20	141	128 – 162
Week 26	183	≥ 163

a: Day 2 assessments are scheduled for specific hours on that day.

Any subject discontinuing prior to Week 1 will have their early termination assessments mapped to Week 1 and not to specific hours on Day 2 regardless of the date.

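### Weekly-average global pain is measured against a single Day 1 score, while knee pain has a 7-day pre-dose mean: a modest, avoidable loss of precision on a secondary endpoint

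*SAP*

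**What the plan says.** SAP 2 has this among the secondary endpoints: "Change from Baseline in the weekly average of daily global pain scores by VAS at Weeks". Week 26 can be read there and the other time points are redacted; the Protocol synopsis names Weeks 12 and 26 and over time. Knee pain has the matching endpoint. Both are 0-100 VAS items with a 24-hour recall (Protocol 7.1).

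SAP 4.10 sets the post-dose quantity for both scores: "Week 1 will be calculated from VAS scores collected on Days 2 through 8, Week 2 from Days 9 through 15, etc". Each weekly mean is taken over the days that have a score.

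The baselines differ:

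- **Global pain (SAP 4.10):** "Daily VAS global pain score is only collected prior to dosing on Day 1". The final score before the time of injection serves as the baseline.
- **Knee pain (SAP 4.10):** "Daily VAS knee pain score is collected daily leading up to Day 1". The baseline is a mean over that run-in, with Day 1 counted only when its score precedes the injection.

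SAP 5.1 agrees. It names knee VAS as the one averaged baseline: "Baseline daily VAS knee pain score will be calculated as the average of the assessments on Day 1 and the previous six days". Every remaining parameter takes its latest available pre-dose reading, and unscheduled readings count. SAP 4.10 also drops any Day 1 score taken after dosing, for either item, from both baseline and Week 1.

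**The concern.** The change score takes one day's reading away from a weekly mean. If pain varies at all from day to day, that reading is a noisier reference and a weaker covariate than a 7-day mean would be. Three things follow.

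- The global pain treatment difference is estimated less precisely than it could have been.
- Within-arm mean change depends on how typical the injection day was of the usual pre-dose week. It cannot be set beside the knee pain change as if the two were built alike.
- If the Day 1 global score is taken after dosing, no earlier scheduled score can replace it. Knee pain would still have up to six days. Protocol 9.7.1 limits change analyses to subjects with both a baseline and a later value, so that subject drops out of the global pain change analysis unless an unscheduled pre-dose score exists.

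**Working it through.** **The plan's own figure.** The visible text gives no SD, power or precision for the global VAS. The only sizing is for WOMAC A in the Protocol synopsis (difference 0.28, SD 0.59, 80% power, about 72 evaluable per arm). It reproduces: 2 × (1.960 + 0.842)² × 0.59² / 0.28² = 69.7, so 70 per arm. It has no bearing on this point.

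**Assumptions (none is in the documents).** Between-subject variance of true pain is 1. A single daily score has reliability r, so daily error variance is w = (1 − r)/r. True baseline and later pain correlate at ρ. Daily errors are independent and all seven days are present. The ranges are r = 0.5 to 0.8 and ρ = 0.5 to 0.7. The reliability of a 7-day mean is R7 = 1/(1 + w/7).

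**Baseline-adjusted analysis.** Residual variance with a 1-day baseline relative to a 7-day baseline is (1 − ρ²·r·R7) / (1 − ρ²·R7²).

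| r | ρ | w | R7 | Variance ratio | SE ratio |
|---|---|---|---|---|---|
| 0.8 | 0.5 | 0.250 | 0.966 | 0.8069/0.7669 = 1.05 | 1.026 |
| 0.6 | 0.6 | 0.667 | 0.913 | 0.8028/0.6999 = 1.15 | 1.071 |
| 0.5 | 0.7 | 1.000 | 0.875 | 0.7856/0.6248 = 1.26 | 1.121 |

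For scale, if the 7-day version had 80% power, the middle row would leave Φ(2.802/1.071 − 1.960) = Φ(0.656), about 74%. The 80% is illustrative, since the visible text claims no power for this endpoint.

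**Unadjusted change score.** The ratio is [2(1 − ρ) + w(1 + 1/7)] / [2(1 − ρ) + 2w/7]. At 0.6/0.6 it is 1.5619/0.9905 = 1.58. Over the same ranges it runs from 1.20 to 1.97. These figures apply only if the model does not adjust for baseline.

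**Autocorrelated daily errors.** If neighbouring days share error, averaging gains less. Replace w/7 by w·k, where k is the mean of φ^|i−j| over the 7 × 7 pairs of days. With lag-1 correlation φ = 0.5, k = 0.348, and the adjusted SE inflation falls to 1.7%-6.0% (4.0% at 0.6/0.6). With φ = 0.7, k = 0.518, and it is 1.2%-3.5% (2.4% at 0.6/0.6).

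**Bias.** A simulation used 72 per arm, 4,000 runs and a true difference of −0.40 daily SD, with same-week correlation between daily scores 0.7 and level correlation 0.6. Either baseline gave about −0.40, adjusted or not. Adjusted SEs were 0.127 (1-day) and 0.120 (7-day); unadjusted SEs were 0.157 and 0.133.

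**What the knee diary can recover.** Let true knee and global pain correlate at c, with knee equally reliable and related to later global pain only through true baseline global pain. With S = [[1 + w, c], [c, 1 + w/7]] and b = (ρ, ρc), residual variance using both covariates is (1 + w/7) − b′S⁻¹b. For c from 0.5 to 0.9, this recovers 14%-68% of the adjusted variance loss at 0.6/0.6, and 7%-73% across the three rows of the table.

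**The case against.** The rule is pre-specified and consistent. Protocol 9.7.1 takes the last pre-dose value as baseline, and SAP 5.1 makes knee VAS the single exception. Baseline knee VAS also has other uses in the visible text, as a covariate (SAP 4.9.1) and a subgroup factor (SAP 4.12), which could explain why only knee pain was collected before Day 1. This is a design choice rather than an analysis error, on one of several secondary endpoints. All of that stands.

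Three stronger readings are tempting, and the documents support none of them.

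- **That the treatment comparison is biased.** Every arm uses the same baseline rule, and the simulation shows no bias.
- **That variance rises by 20%-97%.** This needs an unadjusted change score. The global pain model is not visible, because the covariate list in SAP 4.10 breaks off, and the efficacy models that can be read in full (SAP 3 and 4.9.1) adjust for baseline. The same gap means a knee VAS group term may already be in the global pain model.
- **That there was no reason for the asymmetry.** The schedule of assessments and much of the design text are not visible. One can say only that no reason appears in what remains.

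Timing also limits the remedy. The SAP is dated 30-Sep-2022 and reports the blinded reassessment as already done, which the Protocol places after 80% enrolment. Pre-dose diary days cannot be recovered for subjects already dosed.

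**Conclusion.** The mismatch is stated plainly in SAP 4.10 and 5.1, and some loss of precision follows whenever pain varies from day to day. Under the assumptions above, the loss with baseline adjustment is about 5%-26% in residual variance, or about 3%-12% in standard error (7% at 0.6/0.6), and smaller if daily errors are autocorrelated. The existence of the loss is well supported; its size rests wholly on assumed reliabilities and correlations. The remaining effects are less interpretable within-arm change and a possible missing baseline for a late Day 1 score. It is worth correcting because correction is cheap, but it does not threaten the trial's main conclusion.

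**What to change.** **Where pre-dose data can still be collected** (subjects not yet dosed, or a later protocol): ask the global VAS in the same daily diary as the knee VAS on the six days before Day 1 and on Day 1 before dosing. In SAP 4.10 and 5.1, define baseline global pain as the mean of those days. The cost is one extra question on six days and two sentences in the SAP.

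**For data already collected**, where every subject has only the Day 1 global score:

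- Include for all subjects both the Day 1 global score and the continuous 7-day baseline knee VAS mean as covariates in the global pain model. No new data are needed; the cost is one model parameter and a SAP amendment before unblinding.
- Say how a subject with no pre-dose global score will be handled.
- State that knee and global changes are not to be compared directly in size or precision, because their baselines are built differently.

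While editing, align the knee baseline wording: SAP 4.10 requires the Day 1 score to be pre-dose, and SAP 5.1 omits that condition.

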2 STUDY SYNOPSIS

Name of Sponsor/Company: Sun Pharmaceutical Industries Ltd	Individual Study	(For National Authority Use Only)
Name of Product: MM-II	Table Referring to Part of the Dossier:	
	Volume:	
	Page:	

Title of Study:

A Phase IIb, Randomized, Double-Blind, Placebo-Controlled, Single-administration, Multiple-Dose Study to Demonstrate the Efficacy and Safety of MM-II for Treatment of Knee Pain in Subjects with Symptomatic Knee Osteoarthritis (OA)

Study Centers:

The study will be multinational and multicenter.

Publication(s):

None.

Planned Study Period:	Development Phase:
2020 – 2022	Phase IIb

Objectives:

Primary Efficacy Objective:

 To determine the optimal dose of a single intra-articular (IA) joint injection of MM-II in the treatment of knee pain in subjects with symptomatic knee OA as measured by the change from Baseline of Western Ontario and McMaster Universities Osteoarthritis Index (WOMAC) A pain score at Week 12.

Primary Safety Objective:

To assess the safety and tolerability of a single IA joint injection of MM-II in the treatment of knee pain in subjects with symptomatic knee OA at Week 12.

Secondary Objectives:

- To assess the effect of a single IA joint injection of MM-II in subjects with symptomatic knee
 OA as measured by the change from Baseline for:
 - WOMAC A pain score at Week 26 and over time
 - WOMAC stiffness and disability sub-scores at Weeks 12, 26 and over time
 - The weekly average of daily index knee pain scores by visual analog scale (VAS) at Weeks 12, 26 and over time
 - The weekly average of daily global pain scores by VAS at Weeks 12, 26 and over time
 - Patient Global Assessment (PtGA) of disease activity at Weeks 12, 26 and over time
- To assess the effect of a single IA joint injection of MM-II in subjects with symptomatic OA as compared to placebo at Weeks 12, 26 and over time as measured by the weekly cumulative amount of rescue medication (only acetaminophen/paracetamol allowed)

553	To assess the sa knee pain in sub	fety and tolerability of a single IA joint injection of MM-II in the treatment of ojects with symptomatic knee OA at Week 26 and over time, excluding Week
	12,	
	5.55	
	I	
	ľ	

Methodology:

[figure not shown]

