4.9.1 Sensitivity Analysis

Multiple sensitivity analyses will be performed for the change from Baseline in WOMAC A pain score. One will repeat the primary analysis using the PPAS. The primary analysis will also be repeated for the FAS, but pooling the three placebo groups such that treatment in the model has four levels (1 mL, 3 mL, and 6 mL MM-II and pooled placebo). Comparisons of MM-II will be made against pooled placebo for this analysis.

An additional sensitivity analysis will be performed on the change from Baseline in WOMAC A pain score that imputes missing data using multiple imputations (MI) methodology. For the multiple imputations, subjects on MM-II that discontinue due to lack of efficacy will be imputed according to results for subjects randomized to 3 mL placebo. All other missing data will be imputed according to the subject's randomized treatment.

The multiple imputation method will be applied to missing WOMAC A pain scores from Baseline through Week 12 only. The imputation procedure will first begin by generating 100 imputed datasets for subjects that did not discontinue due to lack of efficacy or that were randomized to placebo. The 100 imputed datasets for the WOMAC A pain scores will be generated separately for each randomized treatment with a fully conditional specification (FCS) model using the regression method. The model will include covariates Baseline BMI group ($<30 \text{ kg/m}^2$, $\geq 30 \text{ kg/m}^2$ and $<35 \text{ kg/m}^2$, $\geq 35 \text{ kg/m}^2$) and Baseline VAS group (≤ 74 , ≥ 75). Following these initial imputations, 100 copies of the non-missing WOMAC A pain scores for subjects on MM-II that discontinue due to lack of efficacy will be generated. One of these copies will be added to each of the 100 imputed datasets generated for the 3 mL placebo group. A single imputation will then be generated for each of these 100 combined sets of data using the same FCS model as above. This will result in 100 imputed datasets for all subjects.

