5.3 Missing Data

WOMAC A pain scores will be imputed as described in Section 4.9.1 for the sensitivity analysis based on multiple imputations. All other analyses will be based on available data. Handling of plasma values that are BQL with respect to the pharmacokinetic analyses are described in Section 4.13.

	CLR_17_17 Statistical Analysis Plan	
	Date: 30-Sep-2022	Page 26 of 28

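### Rescue use between the last scheduled visit and withdrawal is kept out of the rescue MMRM, which may bias that comparison if withdrawal differs by arm and depends on the omitted use

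*SAP*

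**What the plan says.** The protocol synopsis lists weekly cumulative rescue medication as a secondary objective, compared with placebo at Weeks 12, 26 and over time.

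SAP 4.10 builds the measure from the dispensing and accountability eCRF pages. It defines the interval for each visit: "The days associated with a given visit include the date of the previous visit through the day prior to the current visit". Daily doses in the interval are summed, divided by the number of days and multiplied by seven, so every value is a weekly rate whatever the interval's length.

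For subjects who leave early: "Subjects discontinuing early will be analyzed in the MMRM analysis only through the last scheduled visit". The next sentence says that "rescue medication usage after this visit through the date of early termination will be summarized under the heading" Last Visit. The same heading also carries the Week 26 values of completers.

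SAP 5.1 sets the general rule for final assessments of early leavers, which are recorded on the Week 26 eCRFs: "data collected under Week 26 will be mapped to one of the scheduled visits based on the following visit windows". A mapped value is used if that visit has no scheduled result; otherwise it is only listed.

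SAP 5.3 confines multiple imputation to WOMAC A and adds: "All other analyses will be based on available data".

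**The concern.** The omitted stretch lies immediately before withdrawal. If a subject leaves because pain has worsened, it is the stretch most likely to show the rise in rescue use. Without it, the MMRM predicts later use from visits before the worsening, so missing-at-random is harder to defend than it needs to be.

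Pain data are treated differently. Take a subject who attends Week 8 on Day 57 and withdraws on Day 75. The final WOMAC A score falls in the Week 12 window (Days 72–99) and enters the Week 12 analysis. Daily VAS scores are averaged by actual study day, so they are kept up to withdrawal. Rescue use on Days 57–74 does not reach the rescue MMRM. The pain score is modelled and the analgesic use that accompanied it is not.

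The SAP itself foresees withdrawal related to response. In the WOMAC A multiple-imputation analysis, "subjects on MM-II that discontinue due to lack of efficacy will be imputed according to results for subjects randomized to 3 mL placebo". Nothing readable does the same for rescue.

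At stake is one secondary comparison. Use would be understated in the arm with more such withdrawals. If that is placebo, MM-II's benefit on rescue use is understated. If it is an MM-II dose, that dose looks better than it is.

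**Working it through.** **1. The plan's own sample size.** The documents give no power figure for rescue use. For the primary endpoint the protocol synopsis gives a difference of 0.28, SD 0.59, two-sided alpha 0.05, 80% power and 72 evaluable per arm.

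- n = 2 × (1.960 + 0.842)² × (0.59/0.28)² = 69.7, so 70 per arm (71 by the t-test).
- Power at 72: 0.28 / (0.59 × √(2/72)) = 2.85, and Φ(2.85 − 1.96) = 0.813.

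The stated figure reproduces. It is used below only to scale the bias: at 72 per arm the standard error of a difference is √(2/72) = 0.167 SD.

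**2. Length of the omitted interval.** Target days in SAP 5.1 are 8, 15, 29, 57, 85, 113, 141 and 183. The gaps are 7, 14, 28, 28, 28, 28 and 42 days. Up to about four weeks of use can be left out, or six weeks after Week 20.

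**3. When the omission biases the comparison.** No closed formula fits, so this was simulated.

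- Design: two arms, five rescue intervals to Week 12, normal data in SD units, compound symmetry, maximum likelihood equivalent to an unstructured MMRM, 20,000 per arm, 12 replicates, no true difference.
- Assumed, because the documents give no values: withdrawal rates, correlation (0.5 and 0.8), and the log-odds slope of withdrawal on rescue use (1.0 per SD when earlier intervals drive withdrawal; 0.5 to 1.5 when the omitted interval does).

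| What drives withdrawal | Withdrawal, placebo vs active | Bias under SAP 4.10 (SD) | Bias with interval kept (SD) |
|---|---|---|---|
| Nothing related to rescue | up to 30% vs 10% | at most 0.008 | at most 0.008 |
| Earlier, retained intervals | up to 30% vs 10% | at most 0.005 | at most 0.005 |
| Omitted interval | 10% vs 10% | at most 0.006 | at most 0.006 |
| Omitted interval | 15% vs 5% | 0.010 to 0.051 | within 0.005 |
| Omitted interval | 20% vs 10% | 0.019 to 0.051 | within 0.004 |
| Omitted interval | 30% vs 10% | 0.032 to 0.100 | within 0.006 |

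Simulation error is 0.002 to 0.004 SD, so the first three rows are essentially zero. In the last three rows the bias understates the active arm's benefit; by symmetry it reverses if the active arm withdraws more. Adding a true effect of 0.3 SD, with 20% vs 12% withdrawal, correlation 0.65 and slope 1.0, gave 0.025 SD under the plan and −0.003 SD with the interval kept.

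In standard errors, the range is 0.01/0.167 = 0.06 to 0.10/0.167 = 0.6.

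The repair looks complete because withdrawal was made to depend only on an interval that is then retained, and the partial interval was taken to be as informative as a full one. Real rescue data are likely to be skewed and short intervals noisy, so the sizes are indicative.

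**4. Whether the Section 5.1 windows would repair it.** Count the days strictly between target visits from Week 1 to Week 12, and those falling in the window of the visit just attended:

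| Between | Days | Mapped back |
|---|---|---|
| Weeks 1 and 2 (Days 9–14) | 6 | 3 (Days 9–11) |
| Weeks 2 and 4 (Days 16–28) | 13 | 7 (Days 16–22) |
| Weeks 4 and 8 (Days 30–56) | 27 | 14 (Days 30–43) |
| Weeks 8 and 12 (Days 58–84) | 27 | 14 (Days 58–71) |
| Total | 73 | 38 |

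On 38/73 = 52% of these days the termination maps to a visit that already has a value, so the interval would still stay out of the model.

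**The case against.** **Unequal withdrawal is not enough.** A reader might infer that the rule biases the endpoint whenever arms withdraw at different rates. It does not. An MMRM stays close to unbiased at 30% vs 10% if withdrawal is unrelated to rescue use or is driven by intervals still in the model. Dependence on the omitted interval is plausible, but the documents do not establish it.

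**The two sections do not contradict each other.** SAP 5.1 is a general rule for final-visit assessments. SAP 4.10 is an explicit rule for a quantity accumulated over a period and taken from separate eCRF pages. A specific exception is not a conflict. What stands is that no reason for it is readable.

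**The data are not thrown away.** Heavy use before withdrawal would show under Last Visit. That is true, but the row mixes leavers' final intervals with completers' Week 26 values and gives no treatment comparison at Week 12 or 26.

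**Large distortions need strong assumptions.** Suppose mean use is 6.0 vs 4.5 units a week, withdrawal is 15% vs 5%, and every withdrawal starts a lasting rise of 6 units. The Week 12 difference is then −1.50 under the plan against a true −2.11, 29% too small. With a total SD of √(2.5² + 2.0²) = 3.2, that rise is 6/3.2 = 1.9 SD. With a rise of 3 units in half of the withdrawals, the figures are −1.48 against −1.63, or 9% too small. Neither is supported by the documents.

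**Withdrawal may be rare.** If the 348 were split 3:3:3:1:3:1 (an assumption, since the initial ratio is blacked out), each main arm would have 348 × 3/14 = 74.6, and 72 evaluable would imply a loss of 1 − 72/74.6, about 3.4%. The effect would then be small.

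**The rule has a rationale.** It avoids scaling a few days of use to a week, with use on the return day assumed to be nil. This stands, and a minimum-days condition answers it.

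**Part of SAP 4.10 is blacked out.** The full rescue model cannot be seen, and a sensitivity analysis for rescue cannot be ruled out.

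**Conclusion.** The point holds in conditional form. SAP 4.10 leaves the pre-withdrawal interval out of the rescue MMRM although the data are collected and can be expressed as a weekly rate, and nothing readable makes up for it. Bias requires both unequal withdrawal and dependence of withdrawal on use in the omitted interval beyond what earlier intervals predict. Given both, it is about 0.01 to 0.10 SD for withdrawal between 15% vs 5% and 30% vs 10%, or 0.06 to 0.6 standard errors at 72 per arm. If either condition fails, it is near zero.

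These sizes rest on assumed rates, correlations and slopes, and on normal data. The matter is confined to one secondary endpoint, leaves the primary analysis untouched, and is worth correcting mainly because the correction is cheap.

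**What to change.** In SAP 4.10, include the interval from the last attended scheduled visit to early termination in the rescue MMRM as a weekly rate, using the existing formula (sum of daily doses, divided by days, times seven). Assign it to the next unattended scheduled visit. Do not use the Section 5.1 windows, for the reason in step 4 of the working. State a minimum number of days for an interval to qualify, fixed before unblinding. Keep the Last Visit summary.

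If the sponsor prefers to leave the main rescue analysis as it is, prespecify this version as a sensitivity analysis.

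The cost is about one sentence in the SAP and minor programming on data already collected. The drawback is that rates from short intervals are noisier; the minimum-days rule limits this, at the price of still omitting the shortest intervals.
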